NCT04834817 Effect of Combined Red and Near Infrared Light-emitting Diode (LED) Therapy on Tissue Regeneration Post Laser Treatment (Document date: 11/29/2023)

[figure not shown]
STUDY PROTOCOL

Background & Purpose of the Research

The objective of this study is to evaluate the effect of a combination of near infrared (830 nm) red (633 nm) and blue (465nm) light-emitting diode (LED) therapy on wound healing after application of low density ablative fractional laser to bilateral inner biceps, close to the axilla. Our hypothesis is that the LED therapy will result in less post treatment pain and in a faster healing time after ablative fractional laser application.

Literature reveals that light-emitting diodes (LED) promote healing of skin wounds by decreasing inflammation, increasing fibroblast proliferation, stimulating angiogenesis, formation of granulation tissue, and increasing collagen synthesis.1 LED treatment is of interest to the medical community in large part for its safety profile – at 6.5 milliwatts, it emits energy far less than that of a household flashlight. To further determine the extent to which LED promotes healing and to evaluate the relative speed at which it does so compared to other conservative management, this study sets out to assess wound healing with LED treatment after application of fractional ablative laser to the bilateral inner biceps, close to the underarm. Ablative fractional laser treatment results in well-healed regeneration of the superficial layers of the skin, thus an ablative fractional laser with the following parameters will be used to induce a two-inch by two-inch, superficial wound on each ventral bicep: 650 micrometers at 150 J and 5.5% density, similar to parameters used to treat scars. After laser application, we will evaluate the effect of a combination of near infrared (830 nm) red (633 nm) and blue (465nm) light-emitting diode (LED) therapy on wound healing post laser treatment. Product under investigation: BioPhotas Celluma LED device Technical parameters Red: 640nm+/-25nm NIR: 880nm+/-50nm Blue 465nm Irradiance 6.5 mW/cm2 Fluence 11.7J/cm2

Literature reveals that light-emitting diodes (LED) promotes healing of skin wounds by decreasing inflammation, increasing fibroblast proliferation, stimulating angiogenesis, formation of granulation tissue, and increasing collagen synthesis. One proposed mechanism for these changes called the Karu Model is shown below (Figure 1):

Source: Huang YY, et al. 2009.

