Appropriate eye protection in the form of dedicated laser goggles will be provided to the patient and all other individuals in the treatment room. Ablative fractional laser treatment test area will be (5.5% density/700um) delivered to both inner biceps, close to the underarm to an approximately 3 x 3 cm square area. Subjects will evaluate pain and discomfort immediately after the treatment using an 11-point Visual analogue scale. Clinical digital photography of test and control site post induction will be recorded. Immediately after photography the test area will be irradiated with the Biophotas Celluma for 30 minutes. The Celluma light panel will be disinfected prior to every use over open wound. The Control side will be untreated. The Celluma POD device will not be used over known cancer tumor or metastasis.

30 minutes after treatment with the Biophotas Celluma subjects will evaluate pain and discomfort for test and control sites using an 11-point Visual analogue scale.

Days 1-27 – treatment with Celluma

Test site will receive a 30-minute treatment of Celluma, 3 treatments per week for 4 weeks, with the first treatment being day 0 immediately after ablative fractional laser treatment test area. Day 1, 3, 6 subjects will record daily site symptoms including pain and discomfort and complete a treatment log in a patient diary.

Days 2*, 4*, 6*, 9, 13, 20, and 27 – Assessments

* Scheduled follow-up visits may be adjusted 1-2 days based on clinic or patient availability.

Clinical digital photography of test and control site will be recorded. Investigator assessment of treatment response using visual analogue scales to include Time to heal, Percentage healing, edema, erythema, swelling and crusting.

Subject assessment of treatment response using a grading of response.

Day 34 – Assessments Clinical digital photography of test and control site will be recorded. Investigator assessment of treatment response using visual analogue scales to include Time to heal, Percentage healing, edema, erythema, swelling and crusting.

Subject assessment of treatment response using a grading of response.

Day 55 – Final follow up

Clinical digital photography of test and control site will be recorded.

Investigator assessment of treatment response using visual analogue scales to include Time to heal, Percentage healing, edema, erythema, swelling, crusting, discoloration, and scarring

Subject assessment of treatment response using a grading of response.

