If either or both skin wounds have not completely healed by this time, an additional follow-up visit will be scheduled at day 62 (one week after original final follow-up visit).

Study Narrative and Baseline Day 0

- 1. After completing informed consent and photography release forms subjects will be enrolled into the study.
- 2. Subjects will be randomized to which arm denotes the test or control side.
- 3. The clinical investigator will assess baseline characteristics including assessment of Fitzpatrick skin type, ethnicity, demographics and general medical history and status, and concomitant medications.
- 4. Subjects will be instructed on the use of the Biophotas Celluma LED device and observed switching the device ON/OFF, positioning the device and after treatment care of the device.
- 5. Clinical digital photography of treatment site will be recorded immediately prior to treatment
- 6. Ablative fractional laser treatment test area (5.5% density/700um) will be delivered to both inner biceps, close to the underarm an approximately 3×3 cm sq area.
- 7. Immediately after the test area administration, subjects will evaluate pain and discomfort using an 11- point Visual analogue scale.
- 8. Clinical digital photography of test and control site post induction will be recorded.
- 9. Immediately after photography the test wound will be irradiated with the Biophotas Celluma for 30 minutes. The Control side will be untreated. Subjects will be observed self-administrating the treatment.
- 10. 30 minutes after treatment with the Biophotas Celluma subjects will evaluate pain and discomfort for test and control sites using an 11-point Visual analogue scale.
- 11. Subjects will be instructed to treat the test site daily for 28 days and to complete their treatment log and diaries daily. Subjects will be given contact details for any adverse incidents or questions they may have.
- 12. Subjects will be given a date and time to return to the clinic for assessment.

Days 1-27

- 1. Subjects will complete their diaries and treatment log daily.
- 2. Daily, immediately before and 30 minutes after each Biophotas Celluma treatment the subject will record pain and discomfort.
- 3. From Day 2-27 subjects will record itching immediately before and 30 minutes after each Biophotas Celluma treatment.

Days 2*, 4*, 6*, 9, 13, 20 and 27 - Assessments

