Publications and/or presentations that result from this study will not include subject identifiable information.

Time in study 56 days from Baseline visit (day 0)

Study Design

This is a single-center, randomized single-control study. One arm will serve as control and will not receive Celluma LED device treatment. The laterality of the control and test arms will be randomized.

Methods of evaluation

- 1. Fitzpatrick skin typing at baseline including ethnicity
- 2. General medical history and concomitant medications
- 3. Standardized clinical photography
- 4. Investigator assessment of treatment response using applicable scales to include:
 - i. Time to heal
 - ii. Percentage healing
 - iii. Edema iv. Erythema
 - iv. Crusting
 - v. Discoloration
 - vi. Scarring
- 5. Subject assessment of pain, discomfort, and itching post treatment
- 6. Patient diaries
- 7. Adverse event recording

Methods of assessment

Authors note:

Scales used to describe healing in leg ulcers and general or surgical wounds, apart from the Leg Ulcer Measurement Tool LUMT, lack comprehensive and quality evaluation with respect to validity, reliability, and sensitivity. The author has reviewed the Food and Drug Administration's guidelines on wound healing and has identified the following areas that constitute important measurement metrics in wound healing.

Clinical assessment

Clinical photography

Digital clinical photography shall be taken at baseline, immediately post treatment and at each assessment point.

Healing assessment

Clinical assessment shall be performed by independent and blinded assessors, based on visual examination and clinical photography of the test and control areas at baseline (before the first session), and at each assessment point.

Healing shall be graded at each assessment on a 5-point visual analogue scale as follows:

i. Excellent: 81% - 100% healing
ii. Very Good: 61% - 80% healing
iii. Good: 41% - 60% healing
iv. Fair: 21% - 40% healing
v. Little or no change: 0% - 20% healing

Erythema

Clinical assessment shall be performed by independent blinded assessors, based on visual examination and clinical photography of the test and control areas at baseline (before the first session), and at each assessment point.

Erythema shall be graded at each assessment on an 11-point scale as follows:

- i. Little to No Erythema
- 0
- 1

ii. Mild Erythema

- 2
- 3
- 4
- iii. Moderate Erythema
- 5
- 6
- 7

iv. Severe Erythema

- 8
- 9
- 10

Swelling

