Clinical assessment shall be performed by independent and blinded assessors, based on visual examination and clinical photography of the test and control areas at baseline (before the first session), and at each assessment point.

Swelling shall be graded at each assessment on a 11-point scale as follows:

- i. No Swelling evident
- 0
- 1
- ii. Mild Swelling
- 2
- 3
- 4
- iii. Moderate Swelling

- 5
- 6
- 7

iv. Severe Swelling

- 8
- 9
- 10

Crusting

Clinical assessment shall be performed by independent and blinded assessors, based on visual examination and clinical photography of the test and control areas at baseline (before the first session), and at each assessment point.

Crusting shall be graded at each assessment on a 11-point visual analogue scale as follows:

- i. No crusting evident
- 0
- 1

ii. Mild Crusting

- 2
- 3
- 4

iii. Moderate Crusting

- 5
- 6
- 7

iv. Severe Crusting

- 8
- 9
- 10

Subject assessment

Pain

Pain shall be assessed using an 11-point Visual Analogue Scale (VAS) (0-10-point scale). The Scale will be used at the following timepoints.

- i. Immediately after the test area performance
- ii. 30 minutes after the first treatment session of Biophotas Celluma.
- iii. Daily, immediately before and 30 minutes after each Biophotas Celluma treatment.

Discomfort

Discomfort shall be assessed using an 11-point Visual Analogue Scale (VAS) (0-10-point scale). The Scale will be used at the following timepoints.

- i. Immediately after the test area performance
- ii. 30 minutes after the first treatment session of Biophotas Celluma
- iii. Daily, immediately before and 30 minutes after each Biophotas Celluma treatment

Itching

Itching shall be assessed using an 11-point Visual Analogue Scale (VAS) (0-10-point scale). The Scale will be used at the following timepoints.

Daily, immediately before and 30 minutes after each Biophotas Celluma treatment.

STATISTICAL ANALYSIS PLAN

The primary endpoint measured in the study is length of days to reach either a 0 or 1 on the 11-point scale for erythema, swelling, and crusting, as well as 80-100% overall healing on the treatment arm compared to the control arm. Comparisons of pain, discomfort, and itch ratings will also be made between treatment and control arms by calculating the average scores.

Times to full healing and times to resolution of all side effects will be described by frequency distributions together with mean values and associated 95% confidence limits.

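### The protocol gives two incompatible LED schedules for the same four weeks: 12 sessions in one section, 28 in another

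*Combined protocol and SAP*

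**What the plan says.** The LED course is described twice.

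- **Research Procedures, treatment paragraph for Days 1-27:** 30-minute sessions, "3 treatments per week for 4 weeks, with the first treatment being day 0 immediately after ablative fractional laser treatment test area".
- **Study Narrative and Baseline Day 0, item 11:** "Subjects will be instructed to treat the test site daily for 28 days". The same item also has the treatment log and diaries filled in every day.

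The Study Design section makes LED exposure the contrast under test: "One arm will serve as control and will not receive Celluma LED device treatment". Which side is the control is randomized.

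The text on symptom ratings is also uneven. Research Procedures has "Day 1, 3, 6 subjects will record daily site symptoms including pain and discomfort", a sentence that names three days and also says daily. Item 2 under Days 1-27 of the Study Narrative has "Daily, immediately before and 30 minutes after each Biophotas Celluma treatment the subject will record pain and discomfort", and the Pain and Discomfort lists under Subject assessment use the same timing. The SAP then states: "Comparisons of pain, discomfort, and itch ratings will also be made between treatment and control arms by calculating the average scores".

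**The concern.** Each subject is their own control, and LED treatment is the only planned difference between sides. Subjects are trained to run the device themselves, so the instruction they receive largely determines their exposure. If that instruction can be either of two schedules, three things follow.

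- A difference in healing time cannot be attributed to one prespecified regimen.
- The treatment log has no single count to be checked against.
- Any regimen applied uniformly departs from one part of the protocol.

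The symptom data are affected in a lesser way. Ratings are tied to sessions, so the number entering the SAP's averages depends on which schedule was followed.

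**Working it through.** **The plan's own figures first.** The documents state no total number of sessions, so there is none to reproduce. The stated fluence does reproduce as a per-session figure: 6.5 mW/cm2 x 1800 s (30 minutes) = 11.7 J/cm2, as given in the Background. The stated precisions for 25 subjects use 1.96 x SD / sqrt(25), divided by the mean:

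- treated: 1.96 x 1.1 / 5 = 0.431; 0.431 / 13.5 = 3.19% (stated 3.1%)
- untreated: 1.96 x 1.6 / 5 = 0.627; 0.627 / 26.8 = 2.34% (stated 2.3%)
- relative reduction: 1.96 x 2.2 / 5 = 0.862; 0.862 / 50 = 1.72% (stated 1.7%)

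The first is slightly off, and an unrounded SD just under 1.085 would account for it. No session count enters any of these, so the conflict leaves them unchanged.

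**Sessions in the full course.**

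- Research Procedures: 3 x 4 = 12 including day 0, so 11 after day 0.
- Item 11: 28, counting day 0 as the first day, so 27 after day 0. This fits the Days 1-27 headings. Counting from the day after would give 29 in all.
- Difference: 28 - 12 = 16. Ratio: 28/12 = 2.33 (29/12 = 2.42 on the other count).
- Conversely, a subject who follows Research Procedures exactly completes 12/28 = 43% of the item 11 course.

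**Sessions due by the visits that close each week.** This assumes weeks run from day 0, three sessions are completed in each under Research Procedures, and a session on the visit day counts.

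| By day | Research Procedures | Item 11 |
|---|---|---|
| 6 | 3 | 7 |
| 13 | 6 | 14 |
| 20 | 9 | 21 |
| 27 | 12 | 28 |

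**Cumulative exposure**, assuming every session is a full 30 minutes at the stated irradiance: 12 x 11.7 = 140.4 J/cm2 against 28 x 11.7 = 327.6 J/cm2.

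**Can the two texts be read together?**

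- *A clinic and home split:* neither section makes one. There are seven clinic visits from day 2 to day 27; they do not run at three a week, and their listed procedures include no LED session.
- *A different treatment in item 11:* items 4, 9 and 10 around it concern the LED device, and item 11 itself mentions the treatment log.
- *The Days 1-27 heading:* with day 0 it spans 28 days, or four weeks, and so fits both schedules.

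**Ratings (supporting only).** Before-and-after pain ratings following day 0 number 11 x 2 = 22 or 27 x 2 = 54 per site, besides the two day-0 ratings. Rating each site separately is an inference from the SAP's comparison between arms; only the day-0 rating after LED names both sites. The sentence naming days 1, 3 and 6 would give 3 rating days instead of about 11 or 27.

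**The case against.** The conflict itself is hard to dispute; the argument is about how much it matters. Under either schedule the trial still compares LED with no LED within the same person, with side randomized. The SAP plans no adherence, per-protocol or dose-response analysis, so no planned analysis fails. The treatment log allows delivered sessions to be counted afterwards. The 16-session gap also overstates what bears on healing: if treated sites heal at about 13.5 days, the relevant gap is nearer 14 - 6 = 8 sessions.

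Much of this is correct. The within-subject comparison stays valid, and the missing adherence target is a problem of conduct and description. The log is a partial remedy, but a count made afterwards does not restore a prespecified regimen. The smaller gap before healing has the same ratio, 14/6 = 2.33, and shows that the schedules diverge before the primary outcome is expected.

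The rating counts deserve caution. The sentence naming days 1, 3 and 6 is unclear, and the Study Narrative has diaries completed daily whatever the LED frequency, so only the before-and-after ratings need follow the sessions. Nothing in the conclusion depends on them.

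**Conclusion.** The concern holds and needs correction. The two sections cannot both be followed, and the protocol offers no way to choose between them. The ratio of 2.33 rests on day 0 being the first of item 11's 28 days; the alternative count widens the gap slightly and does not remove it. The consequence is limited to what the trial can conclude: LED against no LED can be compared, but the result cannot be assigned to a defined course. The documents do not show which schedule was intended, and this review takes no position on that. The severity rests on the session conflict alone.

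**What to change.** Amend Research Procedures, the Study Narrative and the Subject assessment section so that all three give one session frequency, one total number of sessions and one rating schedule, and match the subject instructions to them. The investigator decides which version stands. If subjects have already been enrolled, document which schedule each was told to follow and report the number of sessions in each log.

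Two separate, smaller items can go in the same amendment. The SAP should say which days, and which of the before and after ratings, enter the average scores; that gap would remain even if the schedules agreed. The Background's wound description ("induce a two-inch by two-inch, superficial wound on each ventral bicep: 650 micrometers at 150 J and 5.5% density") should be reconciled with the area of about 3 x 3 cm and the 700 um setting in the procedural sections.

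The cost is protocol wording, one SAP sentence and a matching instruction sheet.

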A comparable study of LED therapy involving 10 patients gave mean (SD) treated healing time of 13.5 (1.1) days and mean (SD) untreated healing time of 26.8 (1.6) days. Mean (SD) of relative reduction in healing time was 50% (2.2%) and the lowest relative reduction was 48%. Assuming similar results for the proposed study, the study size of 25 would virtually guarantee statistically significant reductions in healing time. Based on 95% confidence intervals, the mean treated healing time, mean untreated healing time and mean relative reduction in healing time will be estimated with precisions of 3.1%, 2.3% and 1.7%.

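### Side is randomised within subject but the planned analysis has no side term; adding one would cost almost nothing and would protect precision if left and right arms differ

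*Combined protocol and SAP*

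**What the plan says.** Each subject has a laser wound on both inner upper arms. The Study Design section says "One arm will serve as control and will not receive Celluma LED device treatment" and "The laterality of the control and test arms will be randomized". The Day 0 steps repeat this: "Subjects will be randomized to which arm denotes the test or control side". No randomisation method, ratio, block size or left/right balance is given.

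For healing time, the SAP says "Times to full healing and times to resolution of all side effects will be described by frequency distributions together with mean values", with 95% confidence limits. Pain, discomfort and itch are compared between arms through average scores. No model, paired test or side term is named.

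The sample-size paragraph rests on an earlier 10-patient study that "gave mean (SD) treated healing time of 13.5 (1.1) days and mean (SD) untreated healing time of 26.8 (1.6) days". It adds: "Mean (SD) of relative reduction in healing time was 50% (2.2%) and the lowest relative reduction was 48" percent. From this it concludes that "the study size of 25 would virtually guarantee statistically significant reductions in healing time", and it gives precisions of 3.1%, 2.3% and 1.7% for treated time, untreated time and relative reduction.

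**The concern.** Randomising laterality creates two groups, test-left and test-right. A systematic left-right difference adds to the control-minus-test difference in one group and subtracts from it in the other, as a period effect does in a two-period crossover. If the analysis ignores the group, this known source of variation is counted as noise.

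What is at stake is the width of the interval for the within-subject effect. Apart from significance, precision is the only numerical aim the plan states. The symptom scores may be more exposed than healing time, because the plan gives no effect size or SD for them.

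**Working it through.** **Inputs from the SAP.** n = 25 pairs; treated mean 13.5 (SD 1.1) days; untreated mean 26.8 (SD 1.6) days; relative reduction 50% (SD 2.2%); 95% intervals.

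**Assumed inputs.** The side difference d is not in the documents. I take 0.5 to 1 day, additive and the same for all subjects, with no dropout.

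**1. The plan's own precisions.** Half-width as a percentage of the mean = 1.96 × SD / √25 / mean.
- Treated: 1.96 × 1.1 / 5 / 13.5 = 3.19%
- Untreated: 1.96 × 1.6 / 5 / 26.8 = 2.34%
- Relative reduction: 1.96 × 2.2 / 5 / 50 = 1.72%

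These match the stated 3.1%, 2.3% and 1.7% if truncated to one decimal, so the inputs are being read as the plan used them.

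**2. Implied within-pair correlation (delta method).** The coefficients of variation are 1.1/13.5 = 0.0815 and 1.6/26.8 = 0.0597, and the mean ratio is 13.5/26.8 = 0.504.
- ρ = [0.0815² + 0.0597² − (0.022/0.504)²] / (2 × 0.0815 × 0.0597) ≈ 0.85
- Paired SD = √(1.1² + 1.6² − 2 × 0.853 × 1.1 × 1.6) = 0.88 day

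**3. Effect of d without a side term.** Each difference is the treatment effect plus or minus d plus error, the sign being set by the randomised side. Under simple randomisation the variance of the mean is (SD² + d²)/25, and the half-width is 2.064 × √(SD² + d²)/5.

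| Paired SD (days) | d (days) | √(SD² + d²) | Half-width (days) | Widening |
|---|---|---|---|---|
| 0.88 | 0 | 0.877 | 0.36 | – |
| 0.88 | 0.5 | 1.009 | 0.42 | 15% |
| 0.88 | 1 | 1.330 | 0.55 | 52% |
| 1.94 (ρ = 0) | 1 | 2.184 | 0.90 | 12% |
| 3 (assumed) | 1 | 3.162 | 1.31 | 5% |

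**4. Uneven split.** With k subjects treated on one side, that trial's estimate moves by d(2k − 25)/25. This is 0.36d at 17:8 and 0.04d at 13:12. If randomisation is simple, 17:8 or worse has binomial probability 10.8%. Over randomisations the shift has mean zero and SD d/5, so its variance is d²/25. That is exactly the term added in step 3.

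**5. Type I error.** In 200,000 simulated trials per scenario (d from 0 to 5 days), an unadjusted paired t-test under simple randomisation rejected in 5.0% to 5.1%. With the split fixed at 13:12 and no side term, it rejected in only 0.4% at d = 1 and SD 0.88. The computed standard error still contains d although the estimate no longer varies with it.

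**6. Power for healing time.** The expected effect is 26.8 − 13.5 = 13.3 days. Using the noncentral t with 24 degrees of freedom and noncentrality 13.3 × 5 / total SD, power falls to 99% at a total SD of 14.9 and to 90% at 19.7. That requires d of about 15 and 20 days.

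**7. Cost of the side term.** At 13:12 the standard error is SD × 0.5 × √(1/12 + 1/13) = 0.2002 SD, against 0.2 SD. The t multiplier goes from 2.064 to 2.069. Together: (0.2002/0.2) × (2.069/2.064) ≈ 1.003, or 0.3% wider if d = 0. Break-even is at d ≈ 0.88 × √(1.003² − 1) ≈ 0.07 day.

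**The case against.** The strongest case against is that the harm rests on a left-right difference that the documents neither report nor assume.
- The possible causes are conjecture. Friction near the axilla affects both arms. Arm dominance is handedness, which is not among the listed baseline assessments, and a left/right term captures it only as far as subjects share handedness.
- Around the expected healing times, visits are 4 to 7 days apart (days 9, 13, 20, 27, 34), so a difference of 0.5 to 1 day is finer than the observation grid.
- The largest widening uses the smallest paired SD.
- The SAP names no within-subject analysis at all, which is the larger gap; a side term only refines it.

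All of this stands. It limits the size of the point and makes the day-level figures approximate. It does not remove the argument that a term costing 0.3% of interval width pays for itself once d exceeds about 0.07 day at the implied SD.

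Three stronger readings are tempting but unsupported:
- **That the sides are unbalanced.** The documents are silent on the method; a blocked list may exist. The 10.8% applies only if randomisation is simple.
- **That omitting side biases the estimate, on top of widening the interval.** Under simple randomisation a 17:8 split is chance imbalance. Its variance is already in the wider interval (at d = 1, a shift of 0.36 day against a half-width of 0.55), so it is the same harm and not a second one.
- **That false positives increase.** Type I error stays near 5%.

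**Conclusion.** The point holds as a low-importance improvement. The plan randomises by side, does not say whether the sides are balanced, and does not use side in the analysis. Under an assumed d of 0.5 to 1 day, the loss is a 15% to 52% wider interval at the implied paired SD of 0.88 day; at d = 1 it is 12% or 5% if the paired SD is 1.94 or 3 days. These figures assume a constant additive d, simple randomisation, no dropout, and a correlation inferred from the 10-patient study.

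A reader might infer that the primary result is at risk. The plan's own figures do not support that: against a 13.3-day effect, significance survives any realistic d. The gain is in precision for healing time and possibly in pain, discomfort and itch, where no SD is given and the benefit cannot be sized.

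**What to change.** - **SAP:** analyse each subject's control-minus-test difference in a linear model with an intercept and side coded +0.5 (test-left) or −0.5 (test-right). The intercept is then the equally weighted average of the two groups' mean differences, on 23 degrees of freedom. Do not centre side at its sample mean, because the intercept then returns the raw mean. With a 17:8 split, a true effect of 13.3 and d = 1, that gives 13.66 instead of 13.30.
- Use the same model for pain, discomfort and itch.
- **Protocol:** state the randomisation method and generate the side list in permuted blocks, giving 12:13. Do this only together with the side term, since balancing alone leaves the computed standard error inflated and the test conservative. The side term does most of the work. Balancing then lowers the standard error by about a further 2% (0.175 against 0.179 at SD 0.88).

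The cost is a sentence or two in each section, one degree of freedom, and intervals about 0.3% wider if there is no side effect.
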